13.5.4 Evaluation of Best Overall Response

The best overall response is the best response recorded from the start of the treatment until disease progression (taking as reference for progressive disease the smallest measurements recorded since the treatment started). The patient's best response assignment will depend on the achievement of both measurement and confirmation criteria.

For Patients with Measurable Disease (e.g., Target Disease)

Target Lesions	Non-Target Lesions	New Lesions	Overall Response	Best Overall Response when Confirmation is Required*
CR	CR	No	CR	≥4 wks. Confirmation**
CR	Non-CR/Non-PD	No	PR	≥4 wks. Confirmation**
CR	Not evaluated	No	PR	
PR	Non-CR/Non-PD/not evaluated	No	PR	
SD	Non-CR/Non-PD/not evaluated	No	SD	documented at least once ≥4 wks. from baseline**

PD	Any	Yes or No	PD	no prior SD, PR or CR
Any	PD***	Yes or No	PD	
Any	Any	Yes	PD	

* See RECIST v1.1 manuscript for further details on what is evidence of a new lesion.
** Only for non-randomized trials with response as primary endpoint (not applicable to this study given PFS6 as primary endpoint).
*** In exceptional circumstances, unequivocal progression in non-target lesions may be accepted as disease progression.

Note: Patients with a global deterioration of health status requiring discontinuation of treatment without objective evidence of disease progression at that time should be reported as “symptomatic deterioration.” Every effort should be made to document the objective progression even after discontinuation of treatment.

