5.2 Intervention

All patients must undergo a mandatory biopsy of a liver lesion prior to chemotherapy initiation. Cycle 1 of chemoimmunotherapy will be administered as per standard of care, with radiation planning to be done subsequently in anticipation of liver-directed SBRT (3 doses of 10 Gy administered on alternating days to up to three liver lesions, measuring no greater than 5 cm each) to be given within +/-3 days of cycle 2.

Subjects will continue to receive study treatment (four 21-day cycles of induction chemoimmunotherapy followed by maintenance atezolizumab every 3 weeks) until disease progression or intolerance of treatment. During the maintenance phase, prophylactic cranial irradiation is permitted; consolidative thoracic radiation may be considered if deemed clinically appropriate by the treating investigator in discussion with the principal investigator.

If clinically feasible, it is recommended that the patient undergo a tumor biopsy sample collection at the time of radiographic disease progression. These data will be used to explore whether radiographic findings are consistent with the presence of a tumor. Additionally, these data will be analyzed to evaluate the association between changes in tumor tissue and clinical outcome and to further understand the potential mechanisms of progression and resistance to study treatment. This exploratory biomarker evaluation will not be used for any treatment-related decisions.

Patients will undergo tumor assessments prior to radiation administration and every 6 weeks (\pm 7 days) for the first 12 months following Cycle 1, Day 1, regardless of treatment dose delays. After 12 months, tumor assessments will be required every 9 weeks (\pm 7 days). Patients will undergo tumor assessments until radiographic disease progression per RECIST v1.1, withdrawal of consent, study termination by the principal investigator, or death, whichever occurs first.

Patients who continue treatment beyond radiographic disease progression per RECIST v1.1 will continue to undergo tumor assessments every 6 weeks (\pm 7 days), or sooner if symptomatic deterioration occurs. For these patients, tumor assessments should continue every 6 weeks (\pm 7 days), regardless of time in the study, until study treatment is discontinued.

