Patients who discontinue treatment for reasons other than radiographic disease progression (e.g., toxicity) will continue scheduled tumor assessments at the same frequency as would have been followed if the patient had remained on study treatment (i.e., every 6 weeks [\pm 7 days] for the first 12 months following Cycle 1, Day 1 and then every 9 weeks [\pm 7 days] thereafter, regardless of treatment dose delays) until radiographic disease progression per RECIST v1.1, withdrawal of consent, study termination by the principal investigator, or death, whichever occurs first, regardless of whether patients start a new anti-cancer therapy.

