13.6 Duration of Response

Duration of overall response: The duration of overall response is measured from the time measurement criteria are met for CR or PR (whichever is first recorded) until the first date that recurrent or progressive disease is objectively documented (taking as reference for progressive disease the smallest measurements recorded since the treatment started).

The duration of overall CR is measured from the time measurement criteria are first met for CR until the first date that progressive disease is objectively documented.

Duration of stable disease: Stable disease is measured from the start of the treatment until the criteria for progression are met, taking as reference the smallest measurements recorded since the treatment started, including the baseline measurements.

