15 STATISTICAL CONSIDERATIONS

15.1 Study Design

This is a single-arm, open-label phase II study to assess the efficacy of liver-directed SBRT added to first-line atezolizumab, carboplatin, and etoposide in ES-SCLC patients as measured by 6-month PFS (primary endpoint). We hypothesize that the addition of SBRT will increase the 6-month PFS from 20% (historical control rate) to 45%. A single-stage design based on one-sided exact binomial test will be used, with a type I error of 0.10 and a power of 80%. This design requires a total of 16 evaluable patients. If at least 6 out of 16 patients have not experienced progression at 6 months, this combination therapy will be considered worthy of further study. In order to account for an estimated 10% dropout rate, 18 patients will be accrued to this study.

Primary endpoint:

- 6-month PFS rate will be defined as the proportion of patients that are progression free and alive at 6 months from the start of treatment.

Secondary endpoints:

- Overall survival (OS) will be defined as the time from treatment start to date of death or last follow up. Patients lost to follow-up at the cut-off date will be censored in the analysis.

- Overall response rate (ORR) will be defined as the proportion of patients who have a partial (PR) or complete response (CR) after beginning study treatment. Only patients who have received at least one cycle of therapy and have had their disease re-evaluated will be considered evaluable for response (see [Section 13.5.2](#)).
- Disease control rate (DCR) will be defined as the proportion of patients who have a partial (PR) or complete response (CR) or stable disease (SD) after beginning study treatment. Only patients who have received at least one cycle of therapy and have had their disease re-evaluated will be considered evaluable for response (see [Section 13.5.3](#)).
- Best overall response (BOR) will be defined as the best response recorded from the start of the treatment until disease progression (see [Section 13.5.4](#)).
- Duration of response will be defined as measured from the time measurement criteria are met for CR or PR until the first date that recurrent or progressive disease is objectively documented (see [Section 13.6](#))
- The safety and tolerability of liver-directed SBRT will be determined by reported AEs, physical examinations and laboratory tests. Frequencies of toxicities by grade according to NCI CTCAE (version 5.0) will be tabulated.

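### Section 13.5.4 leaves the response rules unreconciled: a confirmation sentence that its own footnote disapplies, no minimum for stable disease, and no cut-off when a new anti-cancer therapy starts before progression

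*Combined protocol and SAP*

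**What the plan says.** Section 13.5.4 introduces its response table with an unqualified rule: "The patient's best response assignment will depend on the achievement of both measurement and confirmation criteria". The last column of the table then asks for confirmation after at least 4 weeks in the response rows, and asks that stable disease be "documented at least once ≥4 wks. from baseline". Both kinds of entry carry a double asterisk, and its footnote reads "Only for non-randomized trials with response as primary endpoint (not applicable to this study given PFS6 as primary endpoint". The table gives PD as best response only where no SD, PR or CR came before it.

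The endpoint definitions do not mention confirmation. Section 15.1 has: "Overall response rate (ORR) will be defined as the proportion of patients who have a partial (PR) or complete response (CR) after beginning study treatment". It defines DCR as the "proportion of patients who have a partial (PR) or complete response (CR) or stable disease (SD) after beginning study treatment". Best overall response, in both 13.5.4 and 15.1, runs from the start of treatment to progression. In 13.6, "Stable disease is measured from the start of the treatment until the criteria for progression are met", with no minimum length, and duration of response starts when the measurements first qualify as CR or PR.

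On imaging, Section 5.2 says: "Patients will undergo tumor assessments prior to radiation administration and every 6 weeks", with the first 12 months counted from Cycle 1 Day 1. Patients who stop treatment for a reason other than radiographic progression stay on the same scan schedule "regardless of whether patients start a new anti-cancer therapy".

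**The concern.** There are three gaps in how best response is derived.

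- The general sentence and the footnote in 13.5.4 give opposite instructions on confirmation, and both are current text.
- The footnote that switches off confirmation also switches off the only time requirement for stable disease. No other section supplies one, so any re-evaluation without progression yields SD and counts in DCR.
- The response window has no end at the start of a new anti-cancer therapy. A patient who stops study treatment for toxicity, has not progressed and then responds to another therapy would be counted as a responder to the study regimen.

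ORR is named in the secondary objective (Section 2) as a measure of what liver-directed SBRT adds. There is no control arm, and Section 3 describes the disease as highly sensitive to initial chemotherapy and quick to recur. In a group of about 16, one patient classified differently visibly changes the reported rate. The derivation should therefore be fixed before the data are seen.

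**Working it through.** **The plan's own figures.** No sample size, power or expected value is given for ORR, DCR or BOR. The primary design reproduces: with n = 16 and success at 6 or more, P(X ≥ 6 | p = 0.20) = 0.0817 and P(X ≥ 6 | p = 0.45) = 0.8024, and 16/0.9 = 17.8 rounds up to 18. Nothing below touches these numbers.

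**Step 1, confirmation.** For confirmation: one general sentence in 13.5.4. Against it: the footnote, which speaks of this study and gives a reason; the ORR definition in 15.1, which sets no confirmation condition; and 13.6, which starts the response clock when the measurements first qualify. The weight of text is for unconfirmed ORR. The cross-references in 15.1 do not settle the matter: ORR points to 13.5.2 (non-target lesions) and DCR to 13.5.3 (the radiation field), and neither contains a confirmation rule.

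**Step 2, stable disease and scan timing.** Take Cycle 1 Day 1 as day 1, so C2D1 is day 22 and C4D1 is day 64.

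| Event | Source | Days |
|---|---|---|
| SBRT start | 11.2, C2D1 ± 3 | 19 to 25 |
| SBRT start | calendar note, 7 ± 3 days, if read as after C2D1 | 26 to 32 |
| First 6-weekly scan | 5.2, day 43 ± 7 | 36 to 50 |
| First response scan | 13.1, C4D1 − 7 to C4D1 | 57 to 64 |

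On either SBRT wording, the scheduled response scans come after the start of SBRT given on time. The earliest of them, day 36, is already 36 days after a baseline scan on day −1 (there is no day 0), so the lost 4-week minimum would have been met anyway.

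The gap opens only if the pre-radiation assessment in 5.2 is an on-treatment scan that counts for response. Evaluability in 15.1 needs one cycle and a re-evaluation, not SBRT. A patient with SD on such a scan and PD at the first 6-weekly scan would then have best response SD. Reinstating the 4 weeks from baseline would not reliably close the gap: with baseline on day −28 to −1, a day-22 scan is 22 to 49 days after it.

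**Step 3, new therapy.** Section 5.2 continues scans after a new therapy in patients who stopped without progression. Section 13.5.4 closes the window only at progression. Section 15.1 counts responses from the start of study treatment and names no other end. Together these count a response to the new therapy if it occurs before progression. A response after progression is already outside the window.

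**Step 4, size.** One patient of 16 is 1/16 = 6.25 points. For illustration, assume 10 of 16 respond (62.5%, inside the 60-65% that Section 3 quotes for initial chemotherapy) and let some not be confirmed. Exact (Clopper-Pearson) 95% intervals:

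| Not confirmed | ORR | 95% CI |
|---|---|---|
| 0 | 62.5% | 35.4 to 84.8 |
| 1 | 56.3% | 29.9 to 80.2 |
| 2 | 50.0% | 24.7 to 75.3 |
| 3 | 43.8% | 19.8 to 70.1 |
| 4 | 37.5% | 15.2 to 64.6 |

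These counts are assumed; the documents offer none.

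**The case against.** The footnote is specific to this trial and gives its reason, and the table column it qualifies is headed as applying where confirmation is required. A reader might infer that the plan supports two equally valid ORRs. It does not: the other texts agree on unconfirmed response, and the general sentence looks like a template remnant. This stands. What remains is a sentence that contradicts its own footnote.

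A reader might also infer that DCR can be earned before SBRT, or amounts to surviving the first three weeks of chemotherapy without progression. The documents do not establish that. The study calendar shows CT at screening and C4D1 and none at C2D1, 13.1 begins response scans near C4D1, and the pre-radiation assessment in 5.2 may simply be the screening scan. This also stands. The stable-disease gap is conditional on a reading that the documents neither adopt nor exclude.

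A third tempting inference is that second-line responses in general are credited to the study regimen. They are not. Best response ends at progression, and 8.3 prohibits other anti-cancer therapy during study treatment until progression is documented and treatment has stopped. Only a patient who stops treatment and starts something new before progression is exposed. Sections 6.5.1 and 8.6 could be read as removing such a patient from the study, but 5.2 and the calendar note expressly continue scanning. The narrow gap therefore survives.

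Finally, these are descriptive endpoints reported with confidence intervals, without a test or threshold, and the synopsis calls everything beyond the primary analysis exploratory. That limits the stakes; it does not remove the contradiction.

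**Conclusion.** The point holds in a limited form. Section 13.5.4 contradicts itself on confirmation, with unconfirmed response the better-supported reading. No minimum for stable disease is in force; this has an effect only if an on-treatment scan before radiation counts for response. Responses to a new therapy begun before progression would count in BOR, ORR and DCR, which biases those rates upward.

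The size is 6.25 points per affected patient out of 16. How many would be affected cannot be judged from the documents. The timing conclusion assumes that SBRT is given on schedule: scans follow calendar time from Cycle 1 Day 1 regardless of dose delays, so a late cycle 2 would narrow or reverse the order. The primary endpoint, its sample size and its decision rule are unaffected.

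**What to change.** 1. In 13.5.4 and 15.1, end the best-response window at the earlier of RECIST progression or the start of a new anti-cancer therapy, and apply that window to BOR, ORR and DCR alike.
2. Remove or qualify the confirmation sentence in 13.5.4 so that ORR is unconfirmed, as the footnote and 15.1 imply. List confirmed ORR beside it. Consecutive 6-weekly scans with ± 7-day windows are at least 42 − 14 = 28 days apart, so the existing schedule supports a 4-week confirmation.
3. Count stable disease towards DCR only from the first scheduled 6-weekly response scan onward, so that no pre-radiation scan can earn it. State whether the pre-radiation assessment in 5.2 is the screening scan or an additional one.
4. Reconcile the scan schedule across 5.2, 13.1 and the study calendar. The SBRT timing in 11.2 and in the calendar note must also be reconciled with each other.

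The cost is wording and derivation only, with no extra imaging. ORR and DCR may come out slightly lower, by 6.25 points for each patient reclassified out of 16.

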13.6 Duration of Response

Duration of overall response: The duration of overall response is measured from the time measurement criteria are met for CR or PR (whichever is first recorded) until the first date that recurrent or progressive disease is objectively documented (taking as reference for progressive disease the smallest measurements recorded since the treatment started).

The duration of overall CR is measured from the time measurement criteria are first met for CR until the first date that progressive disease is objectively documented.

Duration of stable disease: Stable disease is measured from the start of the treatment until the criteria for progression are met, taking as reference the smallest measurements recorded since the treatment started, including the baseline measurements.

13.7 Progression-Free Survival

PFS is defined as the duration of time from start of treatment to time of progression as defined by RECIST v1.1 or death, whichever occurs first. The 6-month PFS (PFS6) is defined as the proportion of patients that are progression free and alive at 6 months from the start of treatment.

13.8 Exploratory Biomarkers

An exploratory objective of this study is to identify potential biomarkers of response to the study treatment. Such blood and tissue biomarkers may provide evidence for the synergistic benefit of radiation with chemoimmunotherapy and may inform selection of patients most likely to benefit from this treatment. Biomarker analysis may include PBMC and tumor analyses including but not limited to TCR sequencing, flow cytometry, CITE-SEQ and CyTOF. Tumor specific analyses may

include, but not be limited to, whole exome and RNA sequencing, TCR sequencing, multiplex immunofluorescence analyses.

14 DATA REPORTING / REGULATORY REQUIREMENTS

Adverse event lists, guidelines, and instructions for AE reporting can be found in Section 10.0 (Adverse Events: List and Reporting Requirements). The Data Safety Monitoring Plan is described in Section 14.3.

14.1 Data Collection

The Herbert Irving Comprehensive Cancer Center has an electronic clinical trials and data management system (CTMS) that will be used for data collection. CRFs for the study will be built into the CTMS for data entry. The system has full auditing capabilities which is web-based and housed on a server in a fully HIPAA compliant server room with restricted access and video camera monitoring. All users must login with their own application username and password. Users off campus must first access the Virtual Private Network with their assigned campus username and password and then use their application credentials. Users are only able to see study information if they are indicated as study personnel in our electronic IRB system. Users are limited to access based on the role assigned in their corresponding protocol. Subject data is entered directly into the system, which (in the case of Columbia subjects) confirms the correct identity of patients via an interface with the electronic medical patient index. Staff with the appropriate IRB defined roles can run reports within the system for reporting purposes.

14.2 Data Reporting

Case Report Forms will be completed for each subject enrolled into the clinical study through the CTMS. It is the investigator's responsibility for ensuring that all clinical and laboratory data entered on the corresponding CRFs are complete, accurate and authentic.

14.3 Data and Safety Monitoring Committee

The NCI-approved Data Safety and Monitoring Committee (DSMC) of the Herbert Irving Comprehensive Cancer Center (HICCC) will monitor every subject who receives treatment on this protocol for toxicity. This protocol will adhere to the policies of the currently approved HICCC Data and Safety Monitoring Plan (DSMP), which is in accordance with NCI and CUIMC-IRB policy and guidelines. The committee is chair is appointed by the HICCC Director. The committee consists of HICCC faculty and staff with expertise in oncology, research pharmacy, research nursing, and data management. The DSMC convenes twice a month to review patient safety and the conduct of the trial. The PI will submit data and safety monitoring reports to the DSMC at a frequency to be determined by the DSMC based on risk to the subjects.

At the time of renewal, the study team will submit the most recent DSMC approval letter for safety review to the CUIMC IRB. Any modifications that are required by the DSMC to ensure patient safety will be submitted to the IRB. All protocol deviations, violations, and eligibility waivers will be submitted to and approved by the DSMC prior to being reported to the IRB. All study data reviewed and discussed during these meetings will be kept confidential.

For multicenter research, the principal investigator will assure that there is a mechanism in place to distribute the report to all participating investigators for submission to their local IRB. The report will document that a review of data and outcomes across all centers took place on a given date. It will summarize the DSMC's review of the cumulative toxicities reported from all participating sites without specific disclosure by treatment arm. It will also inform site investigators of the study the DSMC's conclusion with respect to progress or need for modification of the protocol.

14.4 Quality Control and Quality Assurance

Independent monitoring of the clinical study for protocol and GCP compliance will be conducted periodically by the CPDM Compliance Core on behalf of the HICCC DSMC. Additionally, the Compliance Oversight Committee of the IRB at Columbia University Medical Center may audit the study at any time per institutional policies and procedures. The investigator-sponsor and Columbia University Medical Center will permit direct access of the study monitors and appropriate regulatory authorities to the study data and to the corresponding source data and documents to verify the accuracy of this data.

A risk-based approach will be used by the Compliance Core to determine the frequency, number of subject charts, and data elements to be monitored. The Compliance Coordinator will review the study status and summarize enrollment, toxicities, SAEs/UPs, dose escalation, statistical endpoints (e.g., stopping rules), etc. for the full DSMC membership at the regularly scheduled meetings.

Internal On-site Monitoring:

- Initial, recurrent, and close-out on-site monitoring visits will also be conducted at remote clinical sites, as appropriate/feasible. Other sites will have monitoring performed remotely (see below for further details).
- The study Monitoring Visit Log will be completed and signed by the monitor and the PI/CRNP/CRN and/or CRC and will be filed in the regulatory binder.
- The Compliance Coordinator will communicate with the site coordinator/Site Principal Investigator to schedule the monitoring visit and arrange for access to study materials and documentation.
- The assigned Compliance Coordinator will monitor IIT trials within 1 month after the first subject is enrolled and throughout the life of the study to ensure that the study is being conducted in accordance with the protocol, GCP, applicable federal and local regulations, and per all applicable SOPs. The Compliance Coordinator is responsible to notify the PI and CRNP/CRN/CRC of upcoming monitor visits and convey what information and documentation will be required for the visit(s). The Compliance Coordinator is responsible for verifying that informed consent is properly obtained, eligibility is met (via the central registration process), and all study procedures are conducted according to the study protocol. The Compliance Coordinator will also verify that the data reported in the CRF's accurately reflect source

**Columbia University Irving Medical Center
Herbert Irving Comprehensive Cancer Center
CUMC IRB – AAAT0174**

documents, that all toxicities have been reported to date, and that all SAE's/UPs/deviations/violations have been reported according to local IRB and HICCC DSMC requirements. The Compliance Coordinator will issue queries and ensure resolution in a timely and efficient manner. The Compliance Coordinator will also monitor for applicable regulatory compliance and research pharmacy compliance (if applicable) and communicate any deficiencies as appropriate.

